## 8.10 Structured clinical interviews and instruments

Participants will complete the following structured clinical assessments and instruments during the course of the study:

- DSM5 Axis I disorders: *major depressive episode* (current [2 weeks]; past; recurrent); *suicidality* (current [past month]; *panic disorder* (current [past month]; lifetime); *post-traumatic stress disorder* (current [past month]); *generalized anxiety disorder* (current past 6 months); *anti-social personality disorder* (lifetime), via SCID V. Screening and week 36.
- Drug and alcohol use 7 day form- Weeks 1 to 12.
- Minnesota Heroin [adapted] Craving Scale (MCCS for Heroin) Once at screening, then weekly until week 12, once at each follow up visit on weeks 16, 24 and 36 thereafter.
- Minnesota Cocaine [adapted] Craving Scale (MCCS) Once at screening, then weekly until week 12, once at each follow up visit on weeks 16, 24 and 36 thereafter.
- Borderline Personality Disorder Screener (BPD)30\* Screening.
- Short-form Buss-Perry Aggression Questionnaire (BPAQ-SF)31\* Screening.
- Barratt Impulsiveness Scale (BIS-11)32\* Screening.
- Addiction Dimensions for Assessment and Personalised Treatment (ADAPT) Screening, weeks 12 and 36.
- Montreal Cognitive Assessment (MoCA)33. Screening and week 12.
- HIV Risk-taking Behaviour Scale (HRBS) Screening, weeks 12 and 36.
- Scales (TOP) Screening, weeks 12, 36 and at withdrawal.
- Patient Health Questionnaire (PHQ-9) Screening, weeks 12 and 36.
- Generalized Anxiety Disorder Scale (GAD-7) Screening, weeks 12 and 36.
- Work & social adjustment scale (WSAS) Screening, weeks 12 and 36
- EQ5D  Screening, 12 and 36.
- Alcohol and Drug adapted Adult Service Use Schedule (AD-SUS). Screening, 12 and 36.
- Drug and alcohol use 28 day form Screening and weeks 16, 24, and 36 (and at withdrawal if withdrawal is after week 12)
- Heroin use form weeks 24 and 36 (and at withdrawal if withdrawal is after week 12)
- AE & conmed forms Ongoing.

The instruments above marked by an asterisk are for participant self-completion (assisted by a NEAT worker as required). These measures will be gathered and screened in the analysis as moderators of treatment response. The clinical team will use the information collected as part of the case formulation, treatment planning and tailoring process.

## 8.11 Laboratory Tests

Blood samples for hematology and biochemistry analysis will be collected at weeks -2 (unless there is historical blood test less than 2 months old) and then on weeks 4, 8 and 12 thereafter for the following assessments: full-blood count (hematocrit, hemoglobin, red/white blood cell count and platelets); and biochemistry (sodium, potassium, glucose, creatinine, protein, bilirubin, alanine transaminase, aspartate transaminase, gamma-glutamyl transferase, alkaline phosphatase, and creatine phosphokinase).

## 9. Assessment of Effectiveness

A comprehensive analytic strategy will be developed and agreed with the trial's governance committees. Estimates and confidence intervals will be presented for differences over treatment groups. Sensitivity analyses will be used to assess the robustness of conclusions to missing outcome data and to departures from randomized treatment. Loss to follow-up, departures from randomized treatment and the prevalence of serious adverse events will be reported at 1, 3 and 6 months post randomization.

## 9.1 Primary Effectiveness Parameters

The analyses of effectiveness will be pragmatic, based on the intention-to-treat sample, and will utilise all available follow-up data from all randomised patients. The proportion of heroin negative urines at the end of the study period (denominator 36) will be analysed with a regression model adjusted for stratification factors (centre, referral and recent cocaine use) with contrasts for: (i) XR-NTX vs. placebo, and (ii) XR-NTX vs. O-NTX at 12 weeks post-randomisation. The most conservative approach (and used by previous trials) is to record DNA or refused clinic visits and urine samples as positive. A multiple imputation strategy will be approved by the Trial Steering Committee.

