O-NTX has an excellent pharmacological profile as an opioid blocker. However, as a relapse prevention pharmacotherapy it has produced disappointing results. The main reason for this is that patients who succumb to cravings (or are otherwise motivated to use heroin) can relatively easily discontinue their medication and then return to heroin use. Consequently, retention has been shown to be poor in all but the most motivated or socially supported patients. There have been several meta-analyses. In 2006, Berglund and colleagues reported on 10 studies of O-NTX versus control (seven placebo), and six studies of psychosocial/psychopharmacological interventions involving 1,071 patients randomized to oral NTX maintenance therapy for opioid use disorder or a controlxiv. This review pointed to retention as the key variable in explaining NTX's effectiveness. The studies with the highest retention in the experimental group had better results than the control group for differences in retention, opioid-positive urines, psychiatric symptoms and craving for heroin during the experimental period. Among these were those studies which incentivized clinic attendance for each dose by offering vouchers which could be exchanged for recovery appropriate goods or services. In these trials, there was increased retention and a greater reduction in the number of opioid-positive urinesxiv.

In 2007, for a Health Technology Assessment for NIHRxvi, Adi and colleagues reported on 26 studies with 940 participants. They concluded that the methodological quality of the reviewed trials was poor to moderate. Results suggested that O-NTX may be better than placebo in terms of retention in treatment, but overall this was not statistically significant. Among the trials including a contingency management element, the mean length of time patients stayed on NTX was 7.4 weeks, compared with 2.3 to 5.6 weeks on NTX treatment alone. Nevertheless, on the basis of the evidence and clinical experience, NICE recommends that "naltrexone is recommended as a treatment option in detoxified formerly opioid-dependent people who are highly motivated to remain in an abstinence programme"xviii.

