#### 6.2.3 Primary endpoints

*Clinical*: the proportion of heroin negative urines at the end of the 12 week post-randomisation period (denominator 36), with contrasts for: (i) XR-NTX vs. placebo, and (ii) XR-NTX vs. O-NTX.

*Economic*: health related quality of life and cost-effectiveness at 36 weeks.

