#### 12.1 Power calculation

Estimated treatment effect size and retention to guide the required number of participants for NEAT was based on best available trial evidence and meta-analysis. The trial is designed to compare the effectiveness of extended-release naltrexone (XR-NTX) and oral tablet naltrexone (O-NTX) on an intention-to-treat basis at 12 weeks post-randomisation. There are two comparisons: XR-NTX vs. placebo, and XR-NTX vs. O-NTX. Based on a 2007 HTA systematic review and the naltrexone depot trial by [name] and her colleagues in the USA, the following assumptions were made:

- A. The mean percentage of heroin-free urine drug screens at 12 weeks post-randomisation will be approximately 0.30 (30%) in the placebo and O-NTX treatment arms, respectively, and 0.55 (55%) in the XR-NTX treatment 
- B. The standard deviations of the treatment groups will be of a similar magnitude We estimate the common standard deviation to be 30.
- C. The minimal clinically significant difference between the XR-NTX and O-NTX / placebo group will be a 25 point difference in percentage observable at 12 weeks post-randomisation, equating to an effect size of 0.8.
- D. An expected 40% attrition rate based on previous trial data.
- E. To control for multiple comparisons in the primary analyses, Bonferroni correction has been applied to the significance level reducing it by a factor 2. Thus the significance level will be considered at 2.5%.

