## 12.2 Estimated required sample size

With an anticipated 0.8 effect size, a common standard deviation of 30, expected attrition at 40%, and testing significance at 2.5%, a sample size of 300 participants randomized on a 1:1:1 basis to the three arms (100 participants in each arm) will have 98% power to detect a 25 point difference in the percentage heroin-negative urines for the planned comparisons of active treatment arm XR-NTX vs. placebo and active treatment arm XR-NTX vs. standard oral treatment O-NTX.

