## 12.4 Analysis

A comprehensive statistical analysis plan will be be developed and agreed with the trial's oversight committees.

There will be no planned interim analyses. An analysis of the data will be conducted once the trial database has closed. The Data Monitoring Committee will collate effectiveness and safety data during the trial to inform their recommendations to the Trial Steering Committee. A mid-trial formal data analysis is not envisaged.

Statistical analysis will be by intention-to-treat. Descriptive analyses (Q-Q plots, means and standard deviation, median and IQR, or numbers and proportions as appropriate) will be performed for the baseline variables and outcome variables, and will be described by treatment group. The time-to-event outcomes will be explored using life tables and survival plots (Kaplan-Meier curves).

The primary outcome analysis for the effectiveness of XR-NTX vs. placebo, and XR-NTX vs. O-NTX is described in Section 9.1. The secondary outcome analyses are described in Section 9.2.

In the case of missing assessments, such analysis can include these participants provided that prerandomisation values are available for the respective scales. The analysis presumes that the drop-out mechanism is missing at random (MAR). We will examine the scope for using multiple imputation (MI) to generate complete data records as a means of achieving greater efficiency and reduced missing data bias. We will also include as covariates in both model and MI any variables found to be associated with drop-out.

The significance level will be 2.5% (two-sided) for the primary outcome analysis and 5% (two-sided) for secondary outcome analysis. Group difference estimates and associated confidence intervals will be reported. The trial statistician will remain blind whenever possible until the main analyses have been completed.

Loss to follow-up, departures from randomized treatment and the prevalence of serious adverse events will be reported at 12, 16, 24 and 36 weeks post randomization.

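### Section 9.1 leaves two unranked rules for a missed urine sample in the primary endpoint, and the one it calls most conservative is not conservative for a comparison between arms

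*Protocol*

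**What the plan says.** **Endpoint.** Section 6.2.3 defines the clinical primary endpoint as "the proportion of heroin negative urines at the end of the 12 week post-randomisation period (denominator 36"). It is contrasted for XR-NTX versus placebo and XR-NTX versus O-NTX.

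**Missed samples.** Section 9.1 says: "The most conservative approach (and used by previous trials) is to record DNA or refused clinic visits and urine samples as positive". Its next sentence leaves a multiple imputation strategy to Trial Steering Committee approval. Section 9 promises sensitivity analyses for missing outcome data but ties them to neither rule.

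**Missing-data assumption.** Section 12.4 points to 9.1 and 9.2 for the primary and secondary analyses. It then says "The analysis presumes that the drop-out mechanism is missing at random (MAR") and that the scope for multiple imputation will be examined.

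**Covariates.** Section 9.1 adjusts for centre, referral and recent cocaine use. Section 12.4 says: "We will also include as covariates in both model and MI any variables found to be associated with drop-out".

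**Power.** Section 12.1 lists "An expected 40% attrition rate based on previous trial data". Section 12.2 says that 100 per arm "will have 98% power to detect a 25 point difference in the percentage heroin-negative urines". On the test level, 12.4 says: "The significance level will be 2.5% (two-sided) for the primary outcome analysis".

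**The concern.** A missed sample scored positive leaves nothing to impute, and a sample imputed under missing at random is not automatically positive. The two rules give different estimates whenever attendance differs between arms, and 9.1 offers both for the same endpoint without ranking them.

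The label attached to the first rule is also wrong for the purpose it serves. Counting every missed sample as positive is pessimistic about the level in each arm. It is not pessimistic about the difference between arms, which is what both primary contrasts estimate. The arm that attends more gains, so a difference in attendance can be reported as a difference in heroin use. The objective in 6.2.1 is framed as reducing heroin use.

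The covariate sentence in 12.4 is a separate problem. It selects on the data and is not limited to baseline variables. Adjusting for something measured after randomisation could remove part of the treatment effect, and the resulting model is not the one in 9.1.

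**Working it through.** **1. Reproduce the stated power.** Inputs from 12.1, 12.2 and 12.4: difference 25 points, SD 30, effect size stated as 0.8 (25/30 = 0.83), 40% attrition, 100 per arm, two-sided 2.5%.

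- After attrition: 100 × (1 − 0.40) = 60 per arm. The t-test power at d = 0.8 is 98.2% (98.9% at d = 0.83). The stated 98% reproduces.
- With all 100 per arm and d = 0.8, power is 99.96%.

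So the 98% belongs to an analysis that drops 40% of patients, whereas the fixed-36 rule gives all 100 a value.

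**2. Size of the artefact.** Let both arms have the same true negative rate p, and let r_X and r_C be the shares of the 36 samples provided. With missed scored positive, the expected difference in points is

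100 × p × (r_X − r_C).

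The protocol gives neither p nor attrition by arm, so both are assumed: p from 0.3 to 0.7, and retention gaps that keep average retention at the planned 60%.

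- *Largest case:* retention 70% versus 50%, all dropouts leaving before the first sample, p = 0.7: 100 × 0.7 × 0.20 = 14 points, which is 14/25 = 56% of the target difference.
- *Smallest case:* retention 65% versus 55%, dropouts leaving uniformly over the visits, p = 0.3. A uniform dropout supplies about half the samples, so the gap in samples is about 0.05: 100 × 0.3 × 0.05 = 1.5 points.
- *Equal retention:* 0 points.

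**3. False-claim rate.** Simulation with 100 per arm, 36 visits, no effect on use, dropout unrelated to use, and a t-test at two-sided 2.5%. With between-patient SD 0.2 in the negative rate and retention 70% versus 50%:

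| p | Early dropout: difference, rejection | Uniform dropout: difference, rejection |
|---|---|---|
| 0.7 | 13.9 points, 64% | 7.3 points, 34% |
| 0.5 | 10.0 points, 56% | 5.2 points, 24% |
| 0.3 | 6.0 points, 37% | 3.1 points, 13% |

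With between-patient SD 0.3 and uniform dropout, the rates are 22%, 14% and 7% for p = 0.7, 0.5 and 0.3. With retention 65% versus 55% and uniform dropout, they are about 4% to 9% across both SDs. A re-run of the full grid for this write-up gave the same overall range, about 4% to 65%, and about 2.5% when retention was equal.

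As a rough guide, with SD 30 and 100 per arm, significance needs 2.24 × 30 × √(2/100) = 9.5 points. At p = 0.5 that corresponds to a gap in samples provided of 9.5/50, or 19 percentage points.

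**4. Power on the endpoint's own rule.** The answer depends on what the 30% and 55% in 12.1 mean.

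- If they already count missed samples as positive, power with 100 per arm is 99.96% at d = 0.8.
- If they describe attenders and the 40% lost supply no negatives, the means become 0.6 × 30 = 18 and 0.6 × 55 = 33. The variances are 0.6 × 900 + 0.24 × 30² = 756 and 0.6 × 900 + 0.24 × 55² = 1266 (SDs 27.5 and 35.6). Then d = 15/√((756 + 1266)/2) = 0.47, and power is 85.8%.

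**The case against.** **The text is softer than two commands.** Section 9.1 says what the most conservative approach is, not that it will be used, and imputation may have been meant as the sensitivity analysis. A denominator of 36 is compatible with imputing all 36 results. The missing-at-random passage in 12.4 speaks of pre-randomisation values on scales, which fits questionnaires better than a urine count. All of this stands. A reader might infer that the protocol orders two contradictory primary analyses; what it supports is an unranked choice and a sentence of unclear scope.

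**Ranking rules is often left to the analysis plan.** That is fair for detail. But 9.1 itself sets out both rules and describes one of them wrongly.

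**A retention difference would be visible.** Section 9.2 compares retention by Kaplan-Meier and log-rank, and 12.4 reports loss to follow-up. This helps interpretation but does not correct the primary estimate.

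**Differential retention is not established.** Section 5 says "This review pointed to retention as the key variable in explaining" naltrexone's effectiveness, but that review covers oral naltrexone against control. Section 5 also reports that the oral retention advantage over placebo was not significant. All arms here are double-dummy with the same attendance vouchers. A reader might infer that the rule favours XR-NTX. The documents do not support that: section 6.6 cites more implant-site events with active implants, which could push attendance the other way.

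**Missed samples may really be heroin use.** Section 5 says patients can stop oral medication and return to heroin. To that extent the artefact shrinks and part of the difference is real.

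**Post hoc choice.** A reader might infer that the rule could be picked after the data are seen. The text does not show this: committee approval, an agreed analysis plan and a statistician kept blind where possible are all stated.

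**Conclusion.** The point holds in limited form. Section 9.1 does not say which treatment of a missed sample is primary. The conservative label is wrong for a between-arm contrast, because the bias follows attendance and can inflate or mask the effect. As written, the covariate rule in 12.4 differs from 9.1 and is not confined to baseline.

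Over the assumed inputs (negative rate 0.3 to 0.7, retention 65% versus 55% to 70% versus 50%, between-patient SD 0.2 to 0.3, early or uniform dropout), the spurious difference is about 1.5 to 14 points and the false-claim rate about 4% to 65%. The upper end needs a 20-point retention gap, a high negative rate and every dropout leaving before the first sample, so it should not be quoted as the expected error. None of these inputs is in the protocol.

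The power mismatch is secondary. A reader might infer that the trial is underpowered, but no shortfall is shown: 99.96% or 85.8%, the latter only under one assumed reading of 12.1.

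This should be fixed, with moderate confidence. Section 25 records that the trial was wound down with six participants. The point therefore matters mainly for the future trial that section aims to inform.

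**What to change.** - **Section 9.1:** name one primary rule. If it is negatives out of 36 with missed samples counted as not negative, label it a composite of attendance and abstinence. Delete the claim that it is the most conservative approach.
- **Sensitivity analysis:** make the other rule the named sensitivity analysis, with a delta-adjusted or tipping-point range between the two. Report the negative rate among samples provided, and retention by arm, beside the primary result.
- **Section 12.4:** say whether the missing-at-random sentence covers the primary endpoint. Limit the primary outcome model to the three stratification factors, or at most pre-specified baseline covariates. Use predictors of drop-out in the imputation model only.
- **Sections 12.1 and 12.2:** state power on the same rule as the endpoint, and say whether the assumed 30% and 55% already count missed samples as positive.

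The cost is protocol and analysis-plan wording plus the sensitivity analyses. No new data are needed.

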## 9.2 Secondary Effectiveness Parameters

Between treatment retention will be evaluated with Kaplan-Meier curves and log-rank analyses. Adherence will be compared across treatment arms using Chi-square analysis. Other secondary outcomes with repeated measures (such as weekly craving scores; self-reported heroin, cocaine, benzodiazepine, alcohol use) over the 12 weeks will be analysed using longitudinal linear models with adjustment for the stratification factors listed above, treatment arm and baseline values. Chi-squared (Fisher's exact) tests will be used for categorical outcomes (serious adverse events and mortality). Patterns of heroin relapse between treatment arms will be analysed using a latent transitory model

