The majority of individuals presenting to specialist NHS community treatment clinics have established harmful illicit opioid use disorder, almost all related to street heroin. However, the addition of cocaine dependence adds considerable severity to the individual case and this patient sub-group has a relatively poorer outcome compared to primary heroin usersiv. In 2008/09 there were 321,229 individuals in England with problems relating to heroin and/or crack cocaine (corresponding to 9.4 per thousand of the population aged 15-64v). In 2008/09 combined use of heroin and cocaine was reported in 29% of patients admitted for treatmentvi. Intravenous injection is the preferred route of administration by approximately one-third of heroin users, with associated risks of infection and overdose. There are also substantially elevated rates of mood disorders among heroin users compared to the general populationvii, and after opioid detoxification, in addition to craving for heroin, patients often report a syndrome of anhedonia including affective disorders (depression, dysphoria and anxiety). These symptoms may trigger recurrence in heroin useviii.

Study Protocol: Version: 6.0 20.06.2017

The chronic relapsing nature of drug dependence means that helping a patient achieve stable abstinence is often difficult. In the NHS, the front-line clinical response to heroin dependence is the prescription of a substitute (full or partial)  $\mu$ -opioid agonist (oral methadone, oral buprenorphine hydrochloride, or oral buprenorphine-naloxone medication) taken once daily in the context of case management and general counselling support. If the patient receives an appropriate prescribed dose of opioid agonist maintenance therapy, physiological tolerance to opioids is medically managed and there are usually no breakthrough withdrawal symptoms before next dosing. OST medication is administered directly under clinical supervision or by the patient at home.

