#### 12.3 Randomisation

The King's Clinical Trials Unit will oversee randomization. Recruiting centre research staff will randomize participants to one of the three arms of the study (ratio 1:1:1), stratifying by clinical centre, prison or community referral, and recent cocaine use (yes or no) using randomly varying block sizes, via the online randomization system based at King's CTU.

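### Section 9.2 compares retention and adherence without the stratification factors that randomisation and the adjusted analyses use; the tests remain valid but are conservative if those factors are prognostic

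*Protocol*

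**What the plan says.** Retention and adherence form secondary objective A (protocol section 6.2.2). Section 9.2 gives each a named method: "Between treatment retention will be evaluated with Kaplan-Meier curves and log-rank analyses. Adherence will be compared across treatment arms using Chi-square analysis".

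Neither sentence refers to the stratification factors. The following sentence, on the other repeated-measures secondary outcomes, does: they get "longitudinal linear models with adjustment for the stratification factors listed above, treatment arm and baseline values". Section 9.1 adjusts the primary regression for centre, referral and recent cocaine use. Section 12.3 stratifies the 1:1:1 randomisation by the same three factors.

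On reporting, the opening of section 9 states: "Estimates and confidence intervals will be presented for differences over treatment groups". Section 12.4 repeats that commitment directly after setting the two-sided significance level of 5% for secondary outcomes.

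**The concern.** When allocation is balanced within strata and the strata predict outcome, part of the outcome variation is balanced out by design. A test that ignores the strata still counts that variation as noise, so its variance is too large. The type I error then falls below nominal and power is lost. Section 9 avoids this for the primary and repeated-measures outcomes but not for retention and adherence.

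The protocol gives some reason to expect one factor to be prognostic. Section 5 says of patients with added cocaine dependence that "this patient sub-group has a relatively poorer outcome compared to primary heroin" users. What is at stake is some power for secondary objective A, and consistency between adjacent analyses.

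**Working it through.** **1. The protocol's own power figure.** The only stated power is 98% for each primary comparison (section 12.2). Inputs: 100 per arm, 40% attrition, two-sided 2.5%, effect size 0.8.

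- Evaluable per arm: 100 × (1 − 0.40) = 60.
- Power = Φ(d·√(n/2) − z), with z = 2.241 for two-sided 2.5%: 0.8 × √30 = 4.382, and Φ(4.382 − 2.241) = 98.4% (98.2% with the t distribution).

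The 98% reproduces. It concerns the primary outcome only; no power is stated for retention or adherence.

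**2. Three prognostic factors.** Two arms of 100, blocked allocation within 2 × 2 × 2 = 8 strata, exponential drop-out censored at week 12, two-sided 5%, 3,000 runs per setting. The control hazard is centred on 40% drop-out at 12 weeks (−ln 0.6 / 12 per week), taking the attrition figure in section 12.1 as control drop-out. The following are assumed and are not in the protocol: treatment HR 0.55, factor prevalences of 50%, 20% and 30%, the same prognostic HR for each factor, and drop-out by week 12 standing in for binary adherence. CMH is Cochran-Mantel-Haenszel.

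| Prognostic HR per factor | Log-rank power: unstratified / stratified | Chi-square / CMH power | Type I error: unstratified log-rank / chi-square |
|---|---|---|---|
| 1.0 | 67% / 66% | 66% / 66% | 4.9% / 4.8% |
| 1.5 | 66% / 67% | 65% / 66% | 5.0% / 5.2% |
| 2.0 | 65% / 68% | 63% / 67% | 3.6% / 4.4% |
| 3.0 | 58% / 71% | 56% / 66% | 2.6% / 3.1% |

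The stratified tests keep a type I error of 4.7% to 5.5% throughout.

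**3. One prognostic factor.** Cocaine use only, assumed prevalence 40%, treatment HR 0.6, control drop-out fixed at 40%, 4,000 runs per setting.

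| Prognostic HR | Log-rank power: unstratified / stratified |
|---|---|
| 1.5 | 55% / 55% |
| 2.5 | 50% / 53% |
| 4.0 | 47% / 55% |

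**4. Sensitivity to the drop-out rate.** With a baseline hazard of 0.06 per week instead, the log-rank gain is larger: 71% to 77% at HR 2.5 and 67% to 82% at HR 4. Control drop-out is then 1 − 0.6·exp(−12 × 0.06) − 0.4·exp(−12 × 0.06 × HR):

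- HR 1.5: 1 − 0.292 − 0.136 = 57%
- HR 2.5: 1 − 0.292 − 0.066 = 64%
- HR 4: 1 − 0.292 − 0.022 = 69%

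All three are well above the 40% in section 12.1, so steps 2 and 3 are the fairer guide.

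**The case against.** The strongest reply is that the protocol never says the tests are unstratified. It says only log-rank and chi-square, and both section 9 and section 12.4 defer to a fuller analysis plan, where stratifying a secondary log-rank test or coding adherence would normally be settled. This stands in part: unstratified is an inference from silence, and the adherence variable is not defined. But the protocol writes adjustment out wherever it intends it, including in the very next sentence. It also names these two methods instead of leaving them open, so a plan that followed it literally would run unadjusted tests.

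A second reply is that the prognostic strength is unknown. This stands. Section 5 speaks of outcome in general and of cocaine dependence, whereas the stratifier is recent use, yes or no; it gives no figure for retention. The gain therefore has to be read as a range that starts at nothing.

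A reader might also infer two stronger points that the protocol does not support.

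- That retention and adherence will have no effect estimate. Sections 9 and 12.4 promise group differences with confidence intervals. Only the effect measure for these two outcomes is unnamed.
- That interpretation of the primary result is weakened. The primary analysis is already adjusted for the three factors, and a stratified retention test is not a mediation analysis.

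Finally, section 25 records that the decision to wind the trial down was made in November 2016 and that six participants were recruited. Power at 100 per arm is therefore of no practical consequence here; the point is of use to a future trial, which section 25.1 says this experience should inform.

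**Conclusion.** The inconsistency is real and minor. As written, section 9.2 tests secondary objective A without the factors used in randomisation and in the primary and repeated-measures analyses. There is no validity problem: the unadjusted tests hold their level and are conservative when the factors matter.

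With control drop-out near 40%, the gain in log-rank power from using the factors is:

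- negligible at a prognostic HR of 1.5;
- about 3 points at 2 to 2.5;
- roughly 8 to 13 points only at 3 to 4.

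The chi-square to CMH gain runs from 0 to about 10 points over HR 1 to 3. These figures rest on the assumed treatment effects, prevalences and prognostic hazard ratios stated above.

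**What to change.** Amend section 9.2:

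- **Retention:** keep the Kaplan-Meier curves and use a Cox model adjusted for centre, referral and recent cocaine use, reporting the hazard ratio and 95% CI. This also supplies the estimates promised in sections 9 and 12.4. Alternatively, use a log-rank test stratified by those factors that are not sparse. With eight strata and possibly few prison referrals, covariate adjustment is safer than full stratification.
- **Adherence:** use regression adjusted for the same three factors, or Cochran-Mantel-Haenszel if adherence is defined as a category.
- **Contrasts:** state XR-NTX vs placebo and XR-NTX vs O-NTX for both outcomes, matching section 9.1.

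The cost is a sentence or two of text. The factors are already recorded at randomisation, so no new data are needed and the sample size does not change.
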